Official Title: Calibration and Validation of Masimo's O3 Regional Oximetry Device in Neonates, Infants and Children Undergoing Cardiac Catherization

Protocol Date: 2 Dec 2014

NCT Number: NCT03123354

Calibration and Validation of Masimo's O3 Regional Oximetry Device in Neonates,
Infants and Children Undergoing Cardiac Catheterization

Principal investigator: [name]

Abstract:

This study will prospectively collect regional oximetry data from pediatric and neonatal subjects, using a new regional oximetry device (O3™, Masimo, Irvine, CA). The O3 system, consists of a bedside monitor, the POD (cerebral oximetry unit) and near infra-red spectroscopy (NIRS) sensors. To calibrate and validate the technology for cerebral oxygen saturation in this patient population, reference blood samples will be collected from the pediatric subjects who are presenting for diagnostic or therapeutic cardiac catheterization at Stanford University Medical Center.

Purpose:

The aim of the present study is to collect data for calibration and validation of a newly designed O3 cerebral oximeter in pediatric and neonatal patients. Data from cutaneously placed forehead sensors will be continuously collected along with peripheral pulse oximetry. Since cerebral oxygen saturation is a combination of arterial and venous saturations reference blood samples will be collected simultaneously from the artery and the jugular venous bulb.

Background:

Masimo Corporation is the developer of noninvasive technologies for the measurement and monitoring of physiological variables, such as arterial oxygen saturation (SpO₂), total hemoglobin concentration (SpHb), carboxyhemoglobin concentration (SpCO), methemoglobin concentration (SpMet) and acoustic respiration rate monitoring (RRa). These technologies are noninvasive, and have a good patient safety record. This study describes a data collection procedure for the development and calibration of a new regional oximetry system(Masimo $O3^{TM}$) that has originally been developed for adult populations, has received CE mark for use in

the European Union (EU) and is currently pending FDA 510k clearance in the United States for use in adult patients. O3 regional oximetry has recently been evaluated in adult volunteer subjects and found to perform with equivalent or better absolute accuracy and trending accuracy as other commercially available regional oximetry systems.

The O3 regional oximetry sensors contain a 4-wavelength LED emitter, and two light detectors for the detection of deep tissue and superficial oxygenation. The system is designed to allow the near-infrared light to superficially penetrate the scalp, skull and brain tissue. Using multiple wavelengths of light and spatially distributed photo-detectors to interrogate the deep tissue, the O3 system measures regional saturation of oxygen (rSO_2) by establishing a relationship between the light absorbed by the tissue and its oxygen saturation.

The accuracy validation study for the O3 system in an adult population reported a mean bias of 0.4%, absolute root-mean-squared accuracy of 4.0% and trending root-mean-squared accuracy of 2.1%. These accuracy statistics are significantly better than the test accuracy of the most commonly used regional oximeter (INVOS) and match the accuracy of the laser-based Foresight system. The O3 system is much more compact system, technology packed in a small POD.

Finally, the Masimo O3 POD connects to the standard bedside monitor (recently released as Masimo Root that allows simultaneous connection and monitoring of other clinical parameters, including all RainbowSET parameters, SEDLine, Respiration rate, etc., and is configured to connect to 3rd party devices as well).

During data collection, in additional to arterial and venous blood oxygen saturation, other relevant hemodynamic information needs to be recorded. A shift in cerebral vascular tone may change the ratio of arterial to venous blood in the light path.

Because changes in arterial carbon dioxide content are known to change cerebral vascular tone, pH and PCO₂ will be measured and recorded on each blood sample analysis.

LOCATION

The pediatric cardiac catheterization laboratory at Stanford University Medical Center

EQUIPMENT AND MATERIALS

Hospital Standard of Care equipment will be used for the catheterization procedure. In addition the following study specific equipment will be used and supplied by Masimo Corp.

- Masimo O3TM regional oximetry device with forehead sensors and O3TM modules
- Masimo Root Pulse CO-Oximeter and disposable Masimo SET optical sensors Laboratory co-oximeter and blood gas analyzer for determination of arterial (SaO_2) and venous (SvO_2-) and blood gases for pH, pCo2 and PO2

PROCEDURE

- This is a prospective, clinical observational study in pediatric patients with heart disease to collect cerebral recordings of an investigational device sensor (Masimo O3™ regional oximetry system) placed on the subject's forehead as well as oxygen saturation values from arterial blood samples and jugular bulb blood samples for the development and evaluation of algorithms Parental or legal guardian consent and where possible subject assent will be obtained to act as a Human Research Subject prior to being enrolled in the study.
- Demographic information and medical history will be obtained for each enrolled subject prior to the start of the procedure.

An optical finger pulse oximeter sensor to measure SpO2, PI and PR will be placed for continuous monitoring throughout the procedure.

- One or two (depending on size of forehead) Masimo O3[™] cerebral oximetry sensors will be placed on the subjects forehead, then connected to a Masimo Root bedside monitor through a Masimo O3[™] module.
- A laptop with software will be connected to the Root bedside monitor for continuous data collection of all O3 and Masimo SET parameters (SpO2, PR, PI).
- A cardiac catheterization procedure will be performed following institutions standard of care.
- The cardiac interventionist will begin the catheterization process as per standard of care and obtain arterial and venous access. The venous catheter tip will be directed towards the jugular bulb and its correct localization confirmed by fluoroscopy.

samples will be placed in ice and analyzed as soon as possible. The rest of the catheterization procedure will be as per standard of care.

At the conclusion of the study devices and data recording will be stopped,

and study sensors will be removed.

 Subjects will be followed 48 hrs. after the procedure with a phone call to assess any study related adverse event

Subjects

Enrollment will not exceed 50 subjects. This sample size is expected to be sufficient for algorithm development and validation.

Inclusion criteria

- Pediatric patients undergoing cardiac cathetheterization procedure for treatment or diagnosis of cardiovascular disease
- 1 day to less than 18 yrs. of age
- Weight between 3.5 and 40 kg
- parental or legal guardian consent and subject assent

Exclusion criteria

- Failure to obtain written consent
- Equal or more than 18 years in age
- Weigh more than 40 kg or less than 3.5 kg
- Jaundice with bilirubin levels higher than the reference range
- Subject has skin abnormalities affecting the digits such as psoriasis, eczema, angioma, scar tissue, burn, fungal infection, substantial skin breakdown, nail polish or acrylic nails that would prevent monitoring of SpO₂ levels during the study or placement of cerebral oximeter

Measures taken to protect the rights and welfare of subjects

All subjects will be monitored closely throughout the study.

The following measures will be taken to insure the privacy of the subjects:

- A code (identification) number for each subject will be kept on file.
- Only their corresponding identification number will identify subjects.
 - Access to the documents and data will only be made to the investigators in the study.
 - The confidentiality of these documents will be protected to the extent provided by the law.
- Risks, Benefits and Compensation:

- Risks: Noninvasive measurement with cerebral and pulse oximetry: The risk from noninvasive oximetry devices is minimal. The technology uses noninvasive optical sensors.
- Sensor risks: As with all optical sensors, the investigational device has the risk of thermal burn. The design includes safeguards, and this risk is believed to be low. Pressure damage may occur to the tissue if the sensor is placed too tightly. Sensors will be attached with adhesive, and may be secured by a supplemental headband. This risk is believed to be low. Optical exposure is minimized by procedure and low power.
- Benefits: There will be no direct benefits to the enrolled patients. Future benefits to patients might include a reduction in invasive procedures due to the ability to trend moment-by-moment physiological parameters such as regional oximetry.
- Compensation: Study participants will not receive compensation for participation in the study.

References:

- 1. Joebis FF. Noninvasive monitor of cerebral and myocardial oxygen sufficiency and circulatory parameters. Science 1977; 198 (4323): 1264-1267

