## **Applicable Analysis Methods**

Measurement error or bias for the kth sample e(k) is defined as

$$e(k) = rSO_2(k) - SavO_2(k)$$
.

Mean bias over N data points is defined as

$$\mu = \frac{1}{N} \sum_{k=1}^{N} e(k)$$

The Arms can be calculated as

$$A_{rms} \approx \sqrt{\mu^2 + s^2}$$

where s is the estimated standard deviation of bias, accounting for within-subject correlation, which is calculated using the Bland and Altman method for repeated measures. The 95% confidence interval of mean bias was calculated as  $(\mu - 2s/\sqrt{N})$ .

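### Does recording PCO2 at every blood draw oblige the SAP to adjust, or test, the SavO2 reference for it?

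*Protocol*

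**What the plan says.** The Protocol's Purpose section gives the basis for the reference: "Since cerebral oxygen saturation is a combination of arterial and venous saturations", so arterial and jugular bulb blood are drawn together. No weights for the combination are stated there.

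The Background section adds that "A shift in cerebral vascular tone may change the ratio of arterial to venous blood in the light path". It continues that "changes in arterial carbon dioxide content are known to change cerebral vascular tone", and on that ground has pH and PCO2 measured and recorded for each sample analysed. This is presented as relevant haemodynamic information to be captured during data collection.

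The SAP, under Applicable Analysis Methods, introduces its error term with "Measurement error or bias for the kth sample e(k) is defined as" and sets e(k) equal to rSO2(k) minus SavO2(k). Next comes "Mean bias over N data points is defined as", followed by the plain average of the e(k). A_rms is the square root of the squared mean bias plus s². Under Data Analysis, the only adjustment named is for correlation within subjects. Neither section mentions PCO2 or pH, and neither says how SavO2 is built from its two components. An earlier part of the SAP is not visible, so nothing can be said about whether it covers either point.

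**The concern.** Read together, the two documents seem not to join up. The Protocol gives a chain of reasoning (CO2 alters tone, and tone may alter the arterial share) and collects a variable because of it. The SAP then computes accuracy with no term, stratum, plot or sensitivity analysis for that variable.

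The stake would be the reference itself. If the arterial share used in SavO2 differs from the true share for a sample, the discrepancy enters e(k) and is counted as device error. Because the study also serves to calibrate the device, the discrepancy could instead be built into the algorithm and go unseen. The planned handling of repeated measures does not help, since it deals with dependence between samples and not with error in the comparator.

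**Working it through.** The documents give no figure to reproduce here: no weights, no PCO2 range, no arterial-jugular gap, and no link from PCO2 to weight. What can be done is a scale check, followed by a test of what the added analyses would show.

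**Inputs**
- Adult mean bias 0.4 and A_rms 4.0 saturation points (Protocol, Background), used only for scale.
- A_rms = √(μ² + s²) (SAP, Applicable Analysis Methods).
- Assumed: SavO2 = w·SaO2 + (1 − w)·SvO2; error in the arterial weight Δw = 0.02 to 0.10; gap SaO2 − SvO2 = 20 to 40 points.

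**Scale**
1. The adult figures imply s = √(4.0² − 0.4²) = √15.84 = 3.98.
2. An error Δw moves the reference by Δw × (SaO2 − SvO2), whatever the base weight.
3. Two extremes bracket the effect on A_rms. If the shift d is the same in every sample and adds to the bias, A_rms = √((0.4 + d)² + 15.84). If it varies at random between samples with SD d, A_rms = √(0.4² + 15.84 + d²).

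| Δw | Gap | Shift d | A_rms, systematic | A_rms, random |
|---|---|---|---|---|
| 0.02 | 20 | 0.4 | 4.06 | 4.02 |
| 0.05 | 30 | 1.5 | 4.41 | 4.27 |
| 0.10 | 40 | 4.0 | 5.93 | 5.66 |

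The range runs from negligible to as large as the adult A_rms. The systematic column describes a constant that is set wrongly, which is not what the PCO2 argument alleges. Drift with PCO2 varies between samples, partly cancels in the mean and goes mainly into s, so it lies nearer the random column. No entry in the table is tied to any change in PCO2 that the documents report.

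**What the extra analyses would show**
- *Random-intercept model of e(k) on centred PCO2.* The intercept is the bias at mean PCO2. With equal numbers of samples per subject it equals the plain mean bias exactly; otherwise it should be close.
- *The PCO2 slope.* A non-zero slope could mean that the reference drifts with PCO2 or that the device itself responds to CO2. The data contain nothing that separates the two, and that separation is what the concern needs. A single slope would also mix differences between children with changes within a child.
- *Re-scoring at weights 0.05 and 0.10 either side.* Raising the arterial weight by Δw lowers mean bias by Δw × (mean gap), and lowering it does the reverse. A device in perfect agreement with one weighting would show this bias against another. The table would restate the convention; it would not test it.

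**The case for a change.** The best case for a change is that the sponsor itself named the mechanism, the data are already being collected, and the cost is a few lines in the SAP. If the effect may be anything from negligible to as large as the adult A_rms, that uncertainty is itself an argument for a prespecified look. The unadjusted figures could stay as the main result, since performance across the PCO2 values met in practice is part of real performance.

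Much of this is fair. The visible SAP does leave the weights unstated and gives PCO2 no planned use, and a plot or regression of e(k) on PCO2 would do no harm.

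The stronger claims do not stand. The Protocol says that tone may change the ratio; it does not say that PCO2 does. SavO2 is indexed by sample in the SAP, so a single fixed weighting is an inference. The Protocol undertakes to measure and record PCO2, and it makes no commitment to model it, so the two documents do not contradict each other. The visible SAP covers error statistics only, so its silence does not show that PCO2 goes unused in developing the algorithm. Whether a favourable reference could hide bias is a question about keeping calibration and validation data apart, which a PCO2 analysis would not answer.

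The weights do have to be known before any e(k) can be computed. Writing them down is a matter of reporting a definition that the analysts must already hold and that the unseen part of the SAP may contain.

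**Conclusion.** No change to the plan is needed. The observation is accurate as far as the visible text goes, but it identifies an optional exploratory analysis and not an error. No stated figure or rule is shown to be wrong. Mean bias and A_rms would be computed and reported exactly as planned, and none of the proposed additions could attribute a PCO2 pattern to the reference or to the device.

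The size is undetermined: 0.4 to 4.0 points in the reference, and an A_rms of 4.02 to 5.93 against the adult 4.0. This rests on a linear SavO2, on assumed weight errors of 0.02 to 0.10 and gaps of 20 to 40 points, and on adult accuracy carried over to children. With at most 50 subjects, and the number of draws per subject not visible, the precision of any PCO2 slope cannot be judged either.

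Analysts who wish to use the recorded PCO2 can show e(k) against it descriptively, separating variation within and between subjects and giving an interval. They should say that a slope does not identify its cause.

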## **Data Analysis**

We compute error statistics, including mean bias, precision, standard deviation of bias, and absolute root-mean-squared-error accuracy  $A_{rms}$ , accounting for within-subject correlations.

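### Does the SAP need a confidence interval for Arms and for the SD of bias, when the only interval it defines is for mean bias?

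*SAP*

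**What the plan says.** The SAP, Data Analysis, states: "We compute error statistics, including mean bias, precision, standard deviation of bias, and absolute root-mean-squared-error accuracy", and adds that within-subject correlation is allowed for. Applicable Analysis Methods defines the error as the device reading minus the blood reference, gives mean bias as the average error over N data points, and sets Arms equal to the square root of μ² + s². On s it says: "where s is the estimated standard deviation of bias, accounting for within-subject correlation, which is calculated using the Bland and Altman method for repeated measures". One interval follows: "The 95% confidence interval of mean bias was calculated as", and the expression printed after those words is μ − 2s/√N, with no upper limit legible. No interval, standard error or resampling method for Arms or s appears in the supplied SAP text or in the protocol.

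The protocol's Purpose section says: "The aim of the present study is to collect data for calibration and validation". Its Subjects section says: "Enrollment will not exceed 50 subjects", and then: "This sample size is expected to be sufficient for algorithm development and validation". No precision target, power calculation or acceptance limit accompanies that statement.

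**The concern.** Arms combines systematic and random error, and the protocol's Background uses it when comparing oximeters, so readers are likely to look to it for the device's accuracy. When bias is small, Arms is almost entirely s. The adult figures in the Background, "mean bias of 0.4%, absolute root-mean-squared accuracy of 4.0% and trending root-mean-squared accuracy of 2.1" (percent), imply s = √(4.0² − 0.4²) = √15.84 = 3.98, so the bias contributes almost nothing. The plan therefore appears to quantify uncertainty for the minor component and not for the dominant one. Allowing for within-subject correlation when estimating s improves the estimate but does not show how precise it is.

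With at most 50 children, and a protocol that only asserts this number is enough, an interval for Arms would be the direct way to show how well validation succeeded. What is at stake is interpretation: a reported 4.0 could be taken as more exact than it is.

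**Working it through.** **Inputs.** From the protocol: at most 50 children; adult Arms 4.0 and bias 0.4, used here only as a working scale. From the SAP: Arms = √(μ² + s²), with s from the repeated-measures method. Not in the supplied text, so assumed: 1 to 4 draws per child (m), intraclass correlation of the errors (ICC) 0.3 to 0.7, normal errors, bias near zero. There is no stated precision figure to reproduce. The adult numbers do agree with the SAP formula: √(0.4² + 3.98²) = 4.0.

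**Interval with one error per child.** With n independent errors and small bias, the limits are Arms × √(n/χ²), using the 0.975 and 0.025 quantiles on n degrees of freedom.
- n = 50: 4.0 × √(50/71.42) = 3.35 and 4.0 × √(50/32.36) = 4.97.
- n = 25 (if only half the children served validation): 4.0 × √(25/40.65) = 3.14 and 4.0 × √(25/13.12) = 5.52.

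**Interval with repeated draws, 50 children.** Write s² = MSB/m + (1 − 1/m)·MSW, where MSB and MSW are the between- and within-child mean squares. Take Satterthwaite degrees of freedom (df) and chi-square limits. With s² = 16:
- m = 4, ICC 0.3: the terms are 7.6 and 8.4. df = 256/(7.6²/49 + 8.4²/150) = 155.2. Limits: 4.0 × √(155.2/191.6) = 3.60 and 4.0 × √(155.2/122.6) = 4.50.
- m = 2, ICC 0.7: the terms are 13.6 and 2.4. df = 256/(13.6²/49 + 2.4²/50) = 65.8. Limits: 4.0 × √(65.8/90.13) = 3.42 and 4.0 × √(65.8/45.28) = 4.82.
- m = 1: df = 49. Limits: 3.34 and 4.98.

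Simulation of the Arms estimate itself (true SD 4.0, zero bias, 50 children) gives central 95% ranges of 3.58–4.47, 3.36–4.72 and 3.25–4.83 for the same three cases. The uncertainty is therefore real, at roughly −10% to +25% of the estimate with 50 children.

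**What the plan yields if followed as written.** The SAP gives a formula or a named method for mean bias, s and Arms. Nothing above shows those estimates to be biased or any stated number to be wrong. No visible rule compares Arms with a limit, so no conclusion changes according to whether an interval is printed beside it.

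**The bias interval as a benchmark.** Read as μ ± 2s/√N over N data points, its actual coverage with m correlated draws per child is about 2Φ(2/√(1 + (m − 1)·ICC)) − 1.
- m = 2: 2/√1.3 = 1.75 gives 0.92 at ICC 0.3; 2/√1.7 = 1.53 gives 0.87 at ICC 0.7.
- m = 4: 2/√1.9 = 1.45 gives 0.85 at ICC 0.3; 2/√3.1 = 1.14 gives 0.74 at ICC 0.7.

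Simulation agrees (0.920, 0.869, 0.850 and 0.743). The interval for bias is thus not a standard that the treatment of Arms falls short of. Whether it should be computed differently is a separate matter, and an interval for Arms would not settle it.

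**The case for a change.** The strongest case for a change is that a validation study of at most 50 children should show how precisely it estimated its accuracy. The remedy would cost one sentence and no data, and naming the method in advance would prevent a choice made after seeing the results. In simulation with equal draws and zero bias, the variance-components interval for Arms covered 94.7% to 95.3% with 50 children, so a sound method exists.

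Much of this stands. No interval for Arms or s is visible, the sampling error is not trivial, and an interval would help readers. Three things weaken it as a demand on the plan.

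First, absence is not established. Part of the SAP is missing from the supplied text, the list of statistics is open-ended, and the one interval formula shows a single limit, which suggests that text was lost at that very place.

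Second, the SAP lists Arms beside mean bias, precision and SD of bias without ranking it. Treating it as the principal result is a reasonable inference, but the plan does not say so.

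Third, a reader who has Arms and the numbers of children and draws can bracket its uncertainty, as the calculation above does.

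A loosely worded addition would also gain little. With 1 to 4 draws per child at random, a percentile bootstrap over whole children covered s only 89.8% to 92.2% of the time with 50 children and 88.0% to 90.9% with 30. The variance-components interval did better (92.8% to 95.0% and 92.7% to 94.8%), so a sentence allowing either method would not guarantee a good interval.

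**Conclusion.** No change to the plan is needed. The observation is accurate for the supplied text, but it describes a reporting item that analysts can supply sensibly, not an error. Arms and s are validly estimated as written, and no visible decision depends on their intervals. A statistician preparing the report can add an interval from the variance components already behind s, computed on the same errors as the reported Arms, without amending the SAP.

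The size of what would go unreported: for an observed Arms of 4.0 from all 50 children with negligible bias, about 3.6–4.5 (four draws, ICC 0.3) to 3.3–5.0 (one draw). It would be wider if fewer children served validation, for instance 3.1–5.5 with 25 children and one draw each. These figures rest on assumed draws, ICC, normality and the adult value as scale. With zero bias they change in proportion to the true Arms.

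The conclusion would need another look if the missing SAP text set an acceptance limit for Arms, because its precision would then bear on a decision.
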